4.4 Exploratory Endpoints

1. Pain Relief at 15, 30, 45, 60, and 90 minutes, 3, 4, 6, 8, 24, and 48 hours post-dose will be assessed using the number of subjects that report a pain level of moderate or severe at baseline and then report a pain level of none or mild at the timepoint of interest.
2. Pain freedom at 3, 4, 6, 8, 24, and 48 hours post-dose will be assessed using the number of evaluable subjects that report no pain at the timepoint of interest.
3. Freedom from MBS at 3, 4, 6, 8, 24, and 48 hours post-dose will be assessed using the number of evaluable subjects that report the absence of their MBS at the timepoint of interest.
4. The proportion of subjects able to function normally, at all post-dose timepoints except 2 hours, will be assessed using the number of subjects that self-report as “normal” on the FDS in the subset of subjects that report any level of disability just prior to taking study medication.
5. Freedom from phonophobia at all post-dose time points will be assessed using the number of evaluable subjects that report the absence of their phonophobia at the timepoint of interest.
6. Freedom from photophobia at all post-dose time points will be assessed using the number of evaluable subjects that report the absence of their photophobia at the timepoint of interest.
7. Freedom from nausea at all post-dose time points will be assessed using the number of evaluable subjects that report the absence of their nausea at the timepoint of interest.
8. Sustained pain relief from 2 to 24 hours, will be assessed using the number of subjects that report a pain level of none or mild through the time period of interest.
9. Sustained pain relief from 2 to 48 hours, will be assessed using the number of subjects that report a pain level of none or mild through the time period of interest.
10. Freedom from MBS from 2 to 24 hours post-dose will be assessed using the number of evaluable subjects that report the absence of their MBS through the time period of interest.
11. Freedom from MBS from 2 to 48 hours post-dose will be assessed using the number of evaluable subjects that report the absence of their MBS through the time period of interest.
12. The proportion of subjects able to function normally from 2 to 24 hours post-dose, will be assessed using the number of subjects that self-report as “normal” on the FDS through the time period of interest.

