13. The proportion of subjects able to function normally from 2 to 48 hours post-dose, will be assessed using the number of subjects that self-report as “normal” on the FDS through the time period of interest.
14. Time to rescue medication use up to 24 hours pose-dose
15. Time to first report of pain freedom up to 8 hours pose-dose
16. Time to first report of freedom from MBS up to 8 hours pose-dose
17. Time to first report of pain relief up to 8 hours pose-dose
18. Time to first report of absence of nausea up to 8 hours pose-dose
19. Time to first report of absence of photophobia up to 8 hours pose-dose
20. Time to first report of absence of phonophobia up to 8 hours pose-dose
21. Time to first report of return to normal functioning up to 8 hours post dose

5 Sample Size

If roughly 85% of the 715 subjects randomized to each treatment arm have a migraine in the allotted time period, there will be approximately 600 treated subjects per group.

Based on data from studies BHV3000-301 and BHV3000-302, 600 treated subjects provides 95% power to detect a difference between rimegepant and placebo on the subject’s self-reported most bothersome symptom. Also, 600 subjects provides 95% power to detect a difference in freedom from pain at 2 hours. Having at 95% power on each co-primary endpoint provides roughly 90% power to detect a difference on both endpoints jointly.

6 Analysis Sets

The following analysis sets will be evaluated and used for presentation and analysis of the data:

- Enrolled subjects: Subjects who sign an informed consent form and are assigned a subject identification number.
- Randomized subjects: Enrolled subjects who receive a randomization treatment assignment from the IWRS (rimegepant or placebo).
- Treated subjects: Enrolled subjects who take study therapy (rimegepant or placebo).
- Modified Intent to Treat (mITT) subjects: randomized subjects that take study therapy, have a migraine of moderate or severe intensity at the time of treatment, and provide at least one post-treatment efficacy data point.

No separate per protocol analysis set is defined for this study. There will not be any per protocol analysis conducted for this study.

7 Statistical Methods

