7.6 Efficacy Analyses

Unless otherwise noted, all efficacy analyses will be conducted using the mITT population as outlined below. Efficacy tabulations will present results by as-randomized treatment group only (excluding overall), unless specified otherwise. All efficacy data will be included in listings by subject, treatment group, and time point (as applicable).

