7.6.4 Exploratory Efficacy Analyses

7.6.4.1 Binary Exploratory Endpoints

The binary exploratory endpoints will be evaluated using the same methodology described in section 7.6.1.1. The definitions of the binary exploratory endpoints are listed in the table 1 below.

Table 1 Definitions of the Binary Exploratory Endpoints

| Endpoints | Definition of Success | Missing Data or Rescue Medication Handling |
|---|--|--|
| Pain Relief at 15, 30, 45, 60, and 90 minutes, 3, 4, 6, 8, 24, and 48 hours post-dose | Report a pain level of none or mild (responses of 0 or 1 on the 4-point Likert scale) at specified post-dose time point | NC=F; RM=F |
| Pain freedom at 3, 4, 6, 8, 24, and 48 hours post-dose | Report a pain level of none (responses of 0 on the 4-point Likert scale) at specified post-dose time point | NC=F; RM=F |
| Freedom from MBS at 3, 4, 6, 8, 24, and 48 hours post-dose | Report an absence of their MBS (reported at migraine onset) at specified post-dose time point | NC=F; RM=F; IP=F |
| Function normally at all post-dose timepoints except 2 hours | Subjects who report “abnormal” at baseline and have a response of “normal” at specified post-dose time point | NC=F; RM=F |
| Freedom from phonophobia at all post-dose time points | Subject who have phonophobia present at baseline and have absence of phonophobia at specified post-dose time point | NC=F; RM=F |
| Freedom from photophobia at all post-dose time points | Subject who have photophobia present at baseline and have absence of photophobia at specified post-dose time point | NC=F; RM=F |
| Freedom from nausea at all post-dose time points | Subjects who have nausea present at baseline and have absence of nausea at specified post-dose time point | NC=F; RM=F |
| Sustained pain relief from 2 to 24 hours | Subjects that experience no or mild headache pain (response of 0 or 1 on Likert scale) at all time points from 2 through 24 hours post-dose; Subjects with missing pain scores at 1 or fewer | NC1=F; RM=F |

| Endpoints | Definition of Success | Missing Data or Rescue Medication Handling |
|---|---|--|
| | time points, given that they have responses of no or mild pain (response of 0 or 1 on 4-point Likert scale) at all other time points including the 2 and 24 hour post-dose time points, will be considered as successes. | |

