7.6.4.2 Time to Event Endpoints

Time to First Use of Rescue Medication

Kaplan-Meier (K-M) plots will be created for the time to first use of rescue medication. The K-M plot will cover the 24 hour period after dosing. Subjects who did not take rescue medication within 24 hours of dosing will be censored at 24 hours and 1 minute. Regardless of pain or MBS response, subjects are considered at risk until the first use of rescue medication, loss to follow-up (last contact date), or the end of the 24-hour period, whichever comes first. The analysis population consists of mITT subjects.

Two tables will be created to support the plot. The first table presents the median time to rescue medication along with 95% CIs calculated using the method of Brookmeyer and Crowley and the log-rank p-value. The second table presents the number of subjects at risk, with an event, censored, and the survival probability estimate (with 95% CI) from the K-M product limit method for each period (e.g., 0-<2 hours, 2-<4 hours, ..., 20-<22 hours, 22-24 hours) by treatment group.

Time to First Report of Pain Freedom, Pain Relief or Absence of Various Symptoms

For each of the following events, two sets of K-M plots and tables will be created:

- Time to first report of pain freedom up to 8 hours pose-dose
- Time to first report of freedom from MBS up to 8 hours pose-dose
- Time to first report of pain relief up to 8 hours pose-dose
- Time to first report of absence of nausea up to 8 hours pose-dose
- Time to first report of absence of photophobia up to 8 hours pose-dose
- Time to first report of absence of phonophobia up to 8 hours pose-dose
- Time to first report of return to normal functioning up to 8 hours post dose

For both sets of analyses, the analysis population for pain freedom, pain relief and MBS is the set of mITT subjects. The analysis population for nausea, phonophobia, and photophobia is the subset of mITT subjects that reported the symptom as present at the onset of their study migraine. The analysis population for functional disability is the subset of mITT subjects that reported abnormal functioning at the onset of their study migraine.

a) Actual Time for Event of Interest

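### SAP Table 1 gives no denominator for freedom from nausea, photophobia and phonophobia, so the mITT default scores subjects who never had the symptom as failures

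*SAP*

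**What the plan says.** Table 1 in SAP 7.6.4.1 has three columns: endpoint, definition of success, and handling of missing data or rescue medication. None is a denominator. The baseline condition for the three single-symptom rows sits in the success column:

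- Nausea: "Subjects who have nausea present at baseline and have absence of nausea at specified post-dose time point".
- Photophobia: "Subject who have photophobia present at baseline and have absence of photophobia at specified post-dose time point".
- Phonophobia: "Subject who have phonophobia present at baseline and have absence of phonophobia at specified post-dose time point".

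The handling column for these rows gives only NC=F and RM=F. The section opens with "The binary exploratory endpoints will be evaluated using the same methodology described in section 7.6.1.1", and 7.6.1.1 works on mITT subjects. The general rule in SAP 7.6 is "Unless otherwise noted, all efficacy analyses will be conducted using the mITT population as outlined below". The mITT set (SAP section 6) takes randomized subjects who dose, "have a migraine of moderate or severe intensity at the time of treatment, and provide at least one post-treatment efficacy data point"; no associated symptom is required.

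The endpoint list adds little. SAP 4.4 item 7 reads "Freedom from nausea at all post-dose time points will be assessed using the number of evaluable subjects that report the absence of their nausea", and items 5 and 6 match it. The term evaluable is not defined.

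For the time-to-event versions of the same symptoms, SAP 7.6.4.2 does name a subset: "The analysis population for nausea, phonophobia, and photophobia is the subset of mITT subjects that reported the symptom as present" at onset.

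**The concern.** A condition that belongs in the denominator has been written into the numerator. Someone programming from 7.6, 7.6.1.1 and Table 1 would keep every mITT subject in the denominator. A subject with no nausea at dosing would then be a nausea-freedom failure at every time point, whatever happened afterwards.

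Such subjects should be expected. Protocol 1.1 describes migraine as associated with nausea and/or photophobia and phonophobia, and Protocol 6.3.2 records each symptom separately as present or absent.

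The rows cover three symptoms at 12 post-dose times, so 36 comparisons. On the literal reading each reported rate mixes response to treatment with how common the symptom was at onset. That matters here because Protocol 1.3.1 wants the results set beside the earlier program, and Protocol 1.2.3.2 lists photophobia and phonophobia freedom among the earlier findings. There is also a reproducibility cost: two competent programmers could produce different tables from the same text.

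**Working it through.** **1. Reading the text**

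| Analysis | Where the subset is stated | Denominator that results |
|---|---|---|
| Function normally, single time points | SAP 4.2.1 item 2 and 4.4 item 4: disability before dosing | Impaired at baseline |
| Pain relapse | SAP 7.6.3.3: pain free at 2 hours | Stated subset |
| Time to absence of each symptom | SAP 7.6.4.2: symptom present at onset | Stated subset |
| Freedom from each symptom, binary | Not in 4.4 items 5 to 7, nor in 7.6.4.1 | mITT, by the 7.6 default |

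The word evaluable does not settle the last row. SAP 4.1 uses it for the co-primary endpoints, and 7.6.1.1 turns it into mITT subjects. Baseline for efficacy is the assessment at onset of the treated migraine (SAP 7.1), so present at baseline and present at onset mean the same thing.

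**2. Effect of the literal rule**

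Let π be the share of mITT subjects with the symptom at onset, and pT and pC the freedom rates among them.

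- Literal rule: rates π·pT and π·pC on n = 600 per arm; difference π·(pT − pC).
- Subset rule: rates pT and pC on n = 600·π per arm; difference pT − pC.
- Failures by definition per arm under the literal rule: 600·(1 − π).

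**3. Inputs**

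From the documents: about 600 treated subjects per arm (SAP section 5; 0.85 × 715 = 607.75), 1:1 allocation, two-sided alpha 0.05 (SAP 7.6.1.1).

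Assumed, because the documents give no baseline prevalence and no usable rates: pT = 50%, pC = 38%, π from 50% to 85%. The assumed 85% prevalence has nothing to do with the 85% expected to treat a migraine.

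**4. Checking the power formula on the plan's own figures**

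Power = Φ(z − 1.96), with z = (p1 − p0) / √{[p1(1 − p1) + p0(1 − p0)] / n}. For pain freedom at 14% against 22% and n = 600, z = 0.08 / 0.02206 = 3.63 and power is 95.2%; Protocol Appendix IV gives 95.1%. For MBS freedom at 28% against 38% it gives 95.9%; the protocol gives 95.8%. The 0.1-point gaps are consistent with using the unpooled variance in place of the Pearson chi-square calculation.

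**5. Results**

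| π | Failures by definition per arm | Literal rates | Literal difference | Literal z, power | Subset n per arm | Subset difference | Subset z, power |
|---|---|---|---|---|---|---|---|
| 50% | 300 | 25.0% vs 19.0% | 6.0 | 2.52, 71% | 300 | 12.0 | 2.98, 85% |
| 60% | 240 | 30.0% vs 22.8% | 7.2 | 2.84, 81% | 360 | 12.0 | 3.27, 90% |
| 70% | 180 | 35.0% vs 26.6% | 8.4 | 3.16, 89% | 420 | 12.0 | 3.53, 94% |
| 85% | 90 | 42.5% vs 32.3% | 10.2 | 3.67, 96% | 510 | 12.0 | 3.89, 97% |

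The reduction in the difference is exactly 1 − π whatever rates are assumed. The power loss depends on them and nearly vanishes at high prevalence.

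**The case against.** The best reply is that this is a gap in wording and that the SAP means a subset. Much of that stands.

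- **The full mITT denominator is not in Table 1.** It comes only from the default in 7.6. A reader might infer that the SAP has deliberately chosen to count symptom-free subjects as failures; the documents do not support that.
- **The SAP's usage points to a subset.** The single-time-point function row of Table 1 has the same construction, and 4.4 item 4 shows that a subset is meant there. The possessive in 4.4 items 5 to 7 presupposes the symptom, and 7.6.4.2 names the subset for these very symptoms. This makes the intention likely, but the text that governs the binary analysis still does not state it.
- **The table shells may settle it.** SAP section 9 refers to a separate attachment that is not among the documents.
- **The binary and Kaplan-Meier results are separate endpoints.** SAP 4.4 lists them separately. The binary ones run to 48 hours with rescue as failure; the time-to-event ones run to 8 hours with censoring at rescue. Equal denominators would remove one difference between them and would not make them directly comparable.
- **The consequence is small.** The endpoints are exploratory, the plan claims no power for them, and symptom-free subjects fail in both arms, so the literal analysis is still a valid randomized comparison. A chance imbalance in prevalence would add noise, but the test's variance covers that.

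**Conclusion.** The point holds as a specification gap. Followed literally, the SAP scores subjects without the symptom at onset as failures for three exploratory endpoints and scales both rates and the risk difference by baseline prevalence. A symptom-present subset was probably intended but is not stated where it is needed.

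The size is unknown because the documents give no prevalence. Under the assumed 50% versus 38%, it runs from a halved difference and about 14 points of power at 50% prevalence to a loss of 1.8 points of difference and 1 to 2 points of power at 85%.

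A reader might go further and infer a threat to the trial's conclusions or to its error rate. The documents do not support that: the endpoints lie outside the gatekeeping and Hochberg family (SAP 7.3), no co-primary or key secondary result uses them, and the bias is towards a smaller effect. Nor does the point extend to every function endpoint: SAP 4.4 items 12 and 13 state no baseline subset for sustained normal function, and nothing shows that one was meant.

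**What to change.** - In SAP 7.6.4.1 and 4.4 items 5 to 7, set the denominator for the three symptom rows to mITT subjects who reported the symptom as present at onset of the treated migraine. Define success as its absence at the time point. A denominator column in Table 1 would do this.
- State how subjects with no baseline symptom record are handled. SAP 7.7.1 expects some to take study drug before giving baseline migraine characteristics. For MBS the SAP scores them as failures (IP=F), but the symptom rows have no such rule. At present they cannot meet the success definition; under a subset rule they would drop out of the denominator. Either choice should be explicit.
- Repeat the existing subset from 4.2.1 item 2 and 4.4 item 4 in 7.6.2.2 and in the single-time-point function row of Table 1. Leave the sustained-function rows (2 to 24 and 2 to 48 hours) unchanged.
- Check that the table shells agree.

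The cost is SAP wording and, if the shells use the full set, their denominators. No new data are needed, because 7.6.4.2 already relies on the onset record. The downside is fewer subjects in these three analyses, for example 510 per arm instead of 600 at an assumed 85% prevalence.

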7.6.4.2 Time to Event Endpoints

Time to First Use of Rescue Medication

Kaplan-Meier (K-M) plots will be created for the time to first use of rescue medication. The K-M plot will cover the 24 hour period after dosing. Subjects who did not take rescue medication within 24 hours of dosing will be censored at 24 hours and 1 minute. Regardless of pain or MBS response, subjects are considered at risk until the first use of rescue medication, loss to follow-up (last contact date), or the end of the 24-hour period, whichever comes first. The analysis population consists of mITT subjects.

Two tables will be created to support the plot. The first table presents the median time to rescue medication along with 95% CIs calculated using the method of Brookmeyer and Crowley and the log-rank p-value. The second table presents the number of subjects at risk, with an event, censored, and the survival probability estimate (with 95% CI) from the K-M product limit method for each period (e.g., 0-<2 hours, 2-<4 hours, ..., 20-<22 hours, 22-24 hours) by treatment group.

Time to First Report of Pain Freedom, Pain Relief or Absence of Various Symptoms

For each of the following events, two sets of K-M plots and tables will be created:

- Time to first report of pain freedom up to 8 hours pose-dose
- Time to first report of freedom from MBS up to 8 hours pose-dose
- Time to first report of pain relief up to 8 hours pose-dose
- Time to first report of absence of nausea up to 8 hours pose-dose
- Time to first report of absence of photophobia up to 8 hours pose-dose
- Time to first report of absence of phonophobia up to 8 hours pose-dose
- Time to first report of return to normal functioning up to 8 hours post dose

For both sets of analyses, the analysis population for pain freedom, pain relief and MBS is the set of mITT subjects. The analysis population for nausea, phonophobia, and photophobia is the subset of mITT subjects that reported the symptom as present at the onset of their study migraine. The analysis population for functional disability is the subset of mITT subjects that reported abnormal functioning at the onset of their study migraine.

a) Actual Time for Event of Interest

The first set of K-M plots and tables will be created for the above variables using actual time of censoring and actual time for the clinical event of interest. Subjects will be censored at the actual time of their first use of rescue medication or last reported data point if lost to follow-up. Subjects who did not have the clinical event of interest by 8 hours post dose will be censored at 496 minutes (480 minutes + 15 minutes window + 1 minute).

b) Nominal Time for Event of Interest

The second set of K-M plots and tables will be created for the above variables with nominal time (planned time of collection, e.g., 2 hours, 3 hours, etc.) used for clinical events of interest and actual time used for censoring events. Subjects will be censored at the actual time of their first use of rescue medication or last reported data point if lost to follow-up. Subjects who did not have the clinical event of interest by 8 hours post dose were censored at 496 minutes (480 minutes + 15 minutes window + 1 minute).

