9.4.4 Missing Data

As discussed above, missing data for the co-primary endpoints is handled using a composite variable strategy, with missing data imputed to be failure (NC=F). In addition, subjects taking rescue medications prior to reporting their co-primary endpoints will be classified as failure.

The first two key secondary endpoints, pain relief at 2 hours post-dose and the ability to function normally at 2 hours post-dose, are binary endpoints and identical in structure to the co-primary endpoints. Hence, these two key secondary endpoints will be handled with the same composite variable strategy as is applied to the coprimary endpoints.

The third key secondary endpoint, use of rescue medications through 24 hours post-dose will be handled in a similar manner, with NC=F. However, since the use of rescue medications is the endpoint of interest, this is not treated as an intercurrent event.

The fourth and fifth key secondary endpoints, sustained pain freedom from 2 to 24 hours post dose, and from 2 to 48 hours post-dose, are with handled with a similar composite variable strategy. Subjects that use rescue medications before reporting the last data for an endpoint, either at 24 or 48 hours, will be classified as failures. Since subjects will need to sleep over periods as long as 24 or 48 hours, the requirement that non-completers be classified as failures is relaxed slightly. For these variables, subjects with more than 1 missing data point, other than at the critical 2, 24 or 48 hour data points, are classified as failures. For example, for sustained pain freedom from 2 to 24 hours, the subjects are expected to provide data at 2, 3, 4, 6, 8, and 24 hours. The data at 2 and 24 hour time points must be present or the subject is classified as a failure. However, any single data point may be missing at 3, 4, 6 or 8 hours without penalty. For sustained pain freedom from 2 to 48 hours, the data at 2, 24, and 48 hours are required to be present.

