Subjects will record efficacy data in their eDiary. This includes the following: onset time of headache, intensity of the headache prior to and at time of taking study medication. Subject should not dose with study medication until headache reaches moderate to severe intensity. Headache severity will be recorded using a four-point numeric rating scale (no pain, mild pain, moderate pain, severe pain) at the onset of the migraine and after dosing at time points of 15, 30, 45, 60, and 90 minutes and 2, 3, 4, 6, 8, 24 and 48 hours. The presence or absence of associated symptoms (nausea, photophobia, phonophobia) and ratings of functional disability (four-point scale: normal, mildly impaired, severely impaired, requires bedrest) will be recorded at the same time points as the headache severity ratings. Subjects who experience reduction of headache pain to a mild intensity or pain free intensity level will be considered to have achieved pain relief. The subject who does not experience relief of their migraine headache at the end of two hours after dosing with study medication (and after the two hour assessments have been completed on the eDiary) will be permitted to use the following rescue medications: aspirin, ibuprofen, acetaminophen up to 1000mg/day (this includes Excedrin Migraine), naprosyn (or any other type of non-steroidal anti-inflammatory (NSAID)), antiemetics (e.g., metoclopramide or promethazine), or baclofen. These are the only medications allowed for rescue treatment after 2 hours post dose of study medication. If at the end of 48-hours after dosing with study medication (but before the End of Treatment Visit) subjects are in need of migraine relief, they may take their prescribed standard of care medications, including triptans if not contraindicated, provided all of the assessments have been completed on the eDiary. Exclusionary rescue medication such as opioids, ergotamines, butalbital compounds, and muscle relaxants (except baclofen as a rescue medication, see above) are not allowed on this study. Similarly, if the migraine is relieved by study medication at 2 hours after dosing but then recurs to a moderate or severe intensity level between two and forty-eight hours, the subject will be permitted to take the same rescue therapy as outlined above. In all circumstances, the subject will always continue to complete his or her eDiary for up to forty-eight hours after consuming the study medication. During the 45 days the subject is participating in the study, if the subject has a nonqualifying migraine (mild migraine) or a migraine that they do not treat with study medication, the subject is permitted to use only the following medications: aspirin, ibuprofen, naprosyn (or any other type of non-steroidal anti-inflammatory (NSAID)), antiemetics (e.g., metoclopramide or promethazine), or baclofen.

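### First-report Kaplan-Meier curves (SAP 7.6.4.2): a subject who skips the 3 to 8 h diary entries but stays in the study is held at risk to 496 minutes as if observed without the event

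*SAP*

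**What the plan says.** SAP 4.4 lists seven exploratory first-report endpoints (items 15 to 21), the first being "Time to first report of pain freedom up to 8 hours pose-dose". The others cover MBS freedom, pain relief, the three symptoms and normal functioning. SAP 7.6.4.2 analyses each twice: set (a) uses actual event times and set (b) nominal event times, with actual censoring times in both.

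The censoring rules are the same in (a) and (b):
- Earlier than 8 h, two reasons apply: "Subjects will be censored at the actual time of their first use of rescue medication or last reported data point if lost to follow-up".
- Everyone else without an event falls under the end-of-window rule: "Subjects who did not have the clinical event of interest by 8 hours post dose will be censored at 496 minutes". That time is built up as "480 minutes + 15 minutes window + 1 minute".

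The diary schedule in SAP section 3 is "15, 30, 45, 60, and 90 minutes and 2, 3, 4, 6, 8, 24 and 48 hours", so after 2 h the curves rest on the 3, 4, 6 and 8 h entries. No rule covers a subject who skips some of these entries and stays in the study. Loss to follow-up is not defined for these curves; the time-to-rescue curve in the same section ties it to the date of last contact.

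Protocol 9.4.4 recognises gaps in this period, but only for sustained pain freedom: "Since subjects will need to sleep over periods as long as 24 or 48 hours", the non-completer rule is relaxed and "any single data point may be missing at 3, 4, 6 or 8 hours without penalty". More than one missing entry is a failure there.

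**The concern.** A subject who has no event by 2 h, takes no rescue, leaves 3, 4, 6 and 8 h blank and then reports at 24 h or attends the end-of-treatment visit is not lost to follow-up on the natural reading. The 496-minute rule then applies. That subject sits in the risk set at every later event time, exactly as a subject who recorded the symptom at each entry would, but could not have registered an event.

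Contact after the 8 h window therefore decides who is in the risk set inside it. At stake are the later part of the seven curves and any median not reached by 2 h. The Protocol synopsis names time to onset of action as information the study will provide, so these curves are likely to be read.

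**Working it through.** **1. The plan's own figure.** 8 × 60 + 15 + 1 = 496 minutes, which reproduces exactly. The extra 15 minutes admit an 8 h report made late in its window.

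**2. Two subjects with the same data to 8 h.** Both report no event at 2 h, take no rescue and enter nothing at 3, 4, 6 or 8 h.
- Subject A is never heard from again: censored at the 2 h report.
- Subject B reports at 24 h: censored at 496 minutes, so at risk at 3, 4, 6 and 8 h.

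**3. Formula.** Let F2 be cumulative response by 2 h, m the share of 2 h non-responders who miss all four later entries but stay in the study, and h the 2 to 8 h response among those observed. Ignore rescue censoring.
- 496-minute rule: F(8 h) = F2 + (1 − F2)(1 − m)h
- Censoring at the last entry: F(8 h) = F2 + (1 − F2)h
- Difference: (1 − F2) × m × h

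**4. Check by counting.** Take 100 subjects: 20 respond at 2 h, 20 miss all later entries, and of the other 60, 27 respond (7, 7, 7 and 6 at 3, 4, 6 and 8 h).
- 496-minute rule: 47/100 = 47%, no median.
- Last-entry censoring: 1 − 0.80 × 33/60 = 56%. Response is 1 − 0.80 × 39/60 = 48% at 6 h, so the median is 480 minutes.
- Formula: F2 = 0.20, m = 20/80 = 0.25, h = 27/60 = 0.45, so the difference is 0.80 × 0.25 × 0.45 = 9 points, as counted.

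**5. Illustration for pain freedom.** F2 is pooled from Protocol Appendix IV, Table 1:
- rimegepant (104 + 105 + 142)/(543 + 537 + 669) = 351/1749 = 20.1%
- placebo (77 + 64 + 74)/(541 + 535 + 682) = 215/1758 = 12.2%

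These are rates at 2 h, used in place of first report by 2 h. The documents give neither m nor h; h = 0.45 (rimegepant) and 0.30 (placebo) and all values of m are assumptions.

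| m, rimegepant / placebo | Rimegepant, 8 h | Placebo, 8 h | Difference (points) |
|---|---|---|---|
| Last-entry censoring, any m | 56.0% | 38.6% | 17.5 |
| 496 rule, 5% / 5% | 54.2% | 37.2% | 17.0 |
| 496 rule, 10% / 10% | 52.4% | 35.9% | 16.5 |
| 496 rule, 20% / 20% | 48.8% | 33.3% | 15.5 |
| 496 rule, 30% / 30% | 45.2% | 30.7% | 14.6 |
| 496 rule, 20% / 10% | 48.8% | 35.9% | 12.9 |
| 496 rule, 10% / 20% | 52.4% | 33.3% | 19.1 |

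Differences are taken before rounding. With h from 0.30 to 0.60, the rimegepant loss (1 − 0.2007) × m × h is 1.2 to 2.4 points at m = 5% and 7.2 to 14.4 points at m = 30%.

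**6. Medians.** Only a median not reached by 2 h can move. Protocol 1.2.3.1 reports pain relief at 2 h of 72.1% on 75 mg and 51.2% on placebo in the dose-ranging trial. At such rates both pain-relief medians fall at or before 2 h, and later gaps cannot touch them.

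**The case against.** The strongest points on the other side are these.

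- **The key term is undefined.** Loss to follow-up might mean loss of diary data, in which case the skipping subject is censored at the last report. That reading is possible but less natural: the neighbouring rescue curve uses last contact, and these subjects are still in contact. At the least, two programmers could code the rule differently.
- **Missing as non-response is the plan's convention.** The binary endpoints at 3, 4, 6 and 8 h (SAP Table 1) count missing entries as failures. This carries limited weight, because those endpoints also count rescue as failure, whereas the curves censor both rescue and loss. Only gaps within the study are in effect handled as non-response, and the SAP does not say that this is intended.
- **Last-entry censoring makes its own assumption.** It gives skippers the later response rate of those who kept reporting. Missed entries may depend on response. This stands: the assumption is different, not weaker.
- **Set (b) mixes clocks.** A 2 h report made at 115 minutes and used as an actual censoring time would drop the subject before the nominal 120-minute event time. This stands, and the fix must deal with it.
- **Missingness will be tabulated.** SAP 7.6.1.1 and 7.6.1.2 show missing data by time point, and 7.5.6 summarises diary compliance (without 3 h). That helps a reader judge m, but does not correct the curves.

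A reader might also infer that the rule counts sleep as proven lack of response. The documents do not support that. SAP 7.6.4.2 never mentions sleep; the link is an inference from Protocol 9.4.4, which concerns sustained pain freedom and does not say that subjects will miss all four entries. The event is a first report, and these subjects are censored, not scored as failures. A subject who misses 3 to 6 h but reports response at 8 h still counts, only later.

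**Conclusion.** The point holds as a minor one. As written, SAP 7.6.4.2 (a) and (b) keep a subject with unobserved 3 to 8 h entries at risk to 496 minutes, while a subject with the same data who is later lost is censored at the last report.

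The loss in estimated 8 h response is about (1 − F2) × m × h. Its size cannot be fixed from the documents. The formula assumes all four entries are missed and ignores rescue censoring, which removes subjects from later risk sets once rescue is allowed after 2 h.

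Three wider conclusions would be wrong. The gap between arms does not necessarily shrink: that follows in the equal-missingness cases shown, but with unequal missingness the 17.5 points became 12.9 or 19.1. Not every median is delayed, since those reached by 2 h cannot move. And no main result is in doubt: the co-primary and key secondary tests use other rules, these endpoints are exploratory, and none of the 13 exploratory objectives in SAP 2.3 is a time-to-event objective.

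**What to change.** In SAP 7.6.4.2 (a) and (b):

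1. Reserve 496 minutes for subjects without an event or rescue who gave an actual 8 h report.
2. Censor all other subjects without an event or rescue at their last diary assessment at or before the 8 h window, whether or not they are seen later. Loss to follow-up then no longer decides the censoring time.
3. In set (b), censor just after the nominal time of that last assessment, so that it still counts in the risk set.
4. Keep the current 496-minute rule as a sensitivity analysis, because last-entry censoring assumes that missed entries are unrelated to response.

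The cost is a few sentences in the SAP, a programming change and one extra set of curves. Intervals at 6 to 8 h will be wider. No extra data are needed.
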